5.2.1.2 Safety Set (SS) population

The SS will consist of all patients who meet the eligibility criteria and received at least one dose (cycle) of carboplatin AUC-10. Patients who did not receive any doses of study treatment will be excluded from the safety population. All safety analysis will be performed on the SS population.

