##### **4.4.1 *Data collection and follow up for withdrawn subjects***

CRFs should be sent to the Centre for Experimental Cancer Medicine, Barts Cancer Institute within one month of patient completing each cycle.

Subjects who are withdrawn are still evaluable for toxicity and efficacy if they have received at least one cycle of treatment and any data collected whilst receiving treatment will be used in the final analysis. Patients who are withdrawn from the study will be followed up for 2 years after treatment. Similarly, this follow up data will be used in the

final analysis. Any patients who decide to withdraw their consent will have no further data collected unless they have given express permission to do so.

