### **11.3 Statistical Analysis**

All analyses in this study are descriptive and exploratory by nature. Results will be summarised with descriptive statistics (i.e. sample size, mean, and standard deviation, minimum, maximum and median for continuous variables and with tabulations/frequency tables/case listings for categorical variables). Incidence of adverse events will be tabulated. Laboratory data will also be analysed and summarised.

Two analysis sets will be defined:

- The Full Analysis Set (FAS) will consist of all patients who completed at least one cycle of Carboplatin AUC-10 and for whom relevant data is available at baseline and follow up.
- The Safety analysis set (SS) will consist of all patients who received at least one dose of Carboplatin AUC-10.

The FAS will be used for all activity summaries; the SS will be used for all safety summaries. Further descriptions of the statistical analyses will be given in the Study Statistical Analysis Plan, to be finalised prior to database lock.

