### **11.6 Secondary endpoint analysis**

Subgroup analyses of the PFS rate will be performed in terms of patients with complete or partial response at 2 years.

The analysis of safety will include all patients who received at least one cycle of treatment. Safety and tolerability of Carboplatin AUC-10 will be assessed in terms of changes in laboratory parameters, vital signs, the incidence and severity of Adverse Events, and of toxicities according to the CTCAE classification (version 4.03).

The proportion of patients at each toxicity grade (0 to 4) of any type (including vomiting, nausea and diarrhoea) will be summarised. Safety analysis will be performed based on safety data set.

Metabolic response rate will be assessed as described in section 5.3.3.

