5.2.1.1 Full Analysis Set (FAS) population

The FAS will consist of all patients who completed at least one cycle of carboplatin AUC-10 and for whom relevant data is available at baseline and follow up. All efficacy analyses will be performed on the FAS population.

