5.2.2 Protocol Deviations

All-important deviations related to study inclusion or exclusion criteria, conduct of the trial, subject managements or subject assessment will be tabulated and listed.

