5.6 Multiple Testing

[figure not shown]
No adjustment for multiple comparison will be performed.

6 Summary of Study Data

Study data will be summarised using appropriate summary statistics (i.e. mean, standard deviation, median, and range for continuous variables, and number and proportion of patients for categorical variables). Summaries will be presented for the SS population. The baseline value of any variable will be defined as the last available value prior to the first administration of study treatment.

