6.5 Treatment Compliance

Treatment compliance will be presented for all patients in the SS in terms of:

- Median and range for each cycle length.
- Frequency and percentage of patients having a dose reduction.

- Frequency and percentage of patients having a dose reduction due to low platelet count (<20).
- Frequency and percentage of patients discontinuing investigational medicinal product (IMP).
- Frequency and percentage of patients leaving the study due to disease progression or death.

7 Efficacy Analysis

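### The SAP's safety set requires eligibility, which the protocol's safety set and the SAP's own FAS do not, so a treated ineligible patient leaves the safety tables but can still count for PFS

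*SAP*

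**What the plan says.** SAP 5.2.1.2 sets two conditions for the safety set: "The SS will consist of all patients who meet the eligibility criteria and received at least one dose (cycle) of carboplatin AUC-10". It then assigns all safety analysis to that set. The only exclusion it spells out is for patients who received no study treatment.

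The protocol bases safety inclusion on treatment alone. Section 11.3 says: "The Safety analysis set (SS) will consist of all patients who received at least one dose of Carboplatin AUC-10". Section 11.6, and the synopsis in the same terms, says: "The analysis of safety will include all patients who received at least one cycle of treatment". Section 4.4.1 does not define the safety set but points the same way for withdrawals: "Subjects who are withdrawn are still evaluable for toxicity and efficacy if they have received at least one cycle of treatment".

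For efficacy, SAP 5.2.1.1 says: "The FAS will consist of all patients who completed at least one cycle of carboplatin AUC-10", and adds that relevant data must be available at baseline and follow-up. It has no eligibility condition.

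The SS is used beyond toxicity. SAP section 6, which covers disposition and baseline data, says: "Summaries will be presented for the SS population". SAP 6.5 says: "Treatment compliance will be presented for all patients in the SS in terms of" a list that includes dose reductions and discontinuations.

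**The concern.** A safety denominator should be fixed by exposure: whoever received the drug can be harmed by it. The SAP makes it depend also on an eligibility judgement, which may be made after dosing and with the patient's outcome known. The efficacy set does not depend on that judgement. The FAS is therefore not contained in the SS, and one patient can contribute a PFS outcome while his toxicity is missing from the incidence tables.

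Safety and toxicity are part of the first study objective. SAP 5.4 plans no independent data monitoring committee reviews, so the final safety tables carry much of the weight. The SAP states that it is based on protocol version 8.0, and its text gives no reason for narrowing that protocol's safety set.

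**Working it through.** **Step 1. Compare the definitions.**

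| Source | Treatment condition | Eligibility condition |
|---|---|---|
| Protocol 11.3, SS | at least one dose | none |
| Protocol 11.6 and synopsis, safety analysis | at least one cycle | none |
| SAP 5.2.1.2, SS | at least one dose (cycle) | must be eligible |
| SAP 5.2.1.1, FAS | one completed cycle, plus relevant baseline and follow-up data | none |

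Only the SAP's SS has an entry in the last column. A treated ineligible patient who completes one cycle and has the relevant data is in the FAS and outside the SS.

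**Step 2. Can such a patient exist?** SAP 3.2.1 requires all criteria to be met for enrolment, and protocol 10.2 requires 100% source verification of them, so there should be few. Three points show that the case is not excluded:

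- SAP 5.2.2 plans to tabulate and list "All-important deviations related to study inclusion or exclusion criteria", so it allows for them.
- Under protocol 10.2 the first monitoring visit falls within a month of a site's first enrolment, with at least two visits a year during recruitment and treatment. Cycles last 3 weeks, so verification can come after dosing.
- The age limits disagree. Protocol 4.1 includes both 18 and 75; the synopsis and SAP 3.2.1 exclude both. A man exactly at either limit, correctly enrolled under protocol 4.1, fails the SAP's own criterion and would leave the SS. The documents do not say whether age means completed years or exact age, which affects how many men this could touch.

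**Step 3. Size.** The plan has no figure for the safety set to reproduce. Its recruitment target does reproduce: 45 / (1 − 0.10) = 50, and I use 50 as the number treated. The number with an event (x) and the number of treated ineligible patients (k) are assumptions.

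After exclusion, the reported rate runs from (x − k)/(50 − k), if every excluded patient had the event, to x/(50 − k), if none did. Intervals are Clopper-Pearson 95%.

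Common toxicity, x = 10: the full rate is 10/50 = 20.0% (10.0% to 33.7%).

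| k | All excluded had the event | None had it |
|---|---|---|
| 1 | 9/49 = 18.4% | 10/49 = 20.4% |
| 2 | 8/48 = 16.7% | 10/48 = 20.8% |
| 3 | 7/47 = 14.9% | 10/47 = 21.3% |
| 5 | 5/45 = 11.1% | 10/45 = 22.2% |

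Rare event, x = 1: the full rate is 1/50 = 2.0% (0.05% to 10.65%). With k = 1, the table shows either 0/49 = 0.0% (upper limit 1 − 0.025^(1/49) = 7.25%) or 1/49 = 2.04%.

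With k = 0 nothing changes.

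**The case against.** The strongest objection is that the event would not be lost from the trial. SAP 8.3 puts all deaths, serious and other significant events into line listings and reconciles serious events with adverse events. Protocol 8.1 requires the annual risk-benefit analysis to cover all events arising on the trial. This stands in part: a serious event in an ineligible patient could well be visible somewhere. But SAP 8.3 sits within section 8, which is tied to the SS, so it is not a clear exemption, and the incidence tables of SAP 8.2 remain incomplete either way. Protocol 7.6 also exempts expected events, febrile neutropenia among them, from SAE forms and sends them to the notes and CRF, so the adverse event tables are their main outlet.

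A second objection is that the clause may only describe properly enrolled patients, since the next sentence excludes untreated patients alone. That reading is possible but less natural, and the next sentence does not cancel the condition. An ambiguous definition would need the same correction.

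Third, the practical effect may be zero, protocol 11.3 calls all analyses descriptive and exploratory, and the PFS success rule does not use the SS. All of that is true and limits the importance of the point. A patient also reaches the PFS count only if he meets the other FAS conditions and is among the first 45.

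Finally, the age discrepancy exists whatever the SS definition is, and it no longer affects the SS once the clause is removed. That is right; it is a secondary point here.

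**Conclusion.** The concern holds. The mismatch is certain on the text: the SAP narrows the protocol's safety set by eligibility and does not apply the same condition to efficacy. Its effect is uncertain, limited to treated patients judged ineligible, and nil if there are none. For common toxicities one or two exclusions out of 50 would move a rate by at most a few percentage points, well within its sampling error. For a rare event, one exclusion could remove the only case from the incidence table. These sizes rest on assumed event and ineligibility counts. The clause should be corrected because it sets the wrong rule and costs almost nothing to remove; the sample size, error rates and PFS decision rule are not affected.

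**What to change.** In SAP 5.2.1.2, delete the eligibility clause so that the SS depends only on having received at least one dose of carboplatin AUC-10, as in protocol 11.3. Removing the bracketed word for cycle from the same sentence is optional tidying. Keep ineligible patients identified in the deviation table and listing of SAP 5.2.2.

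Add one sentence to the SAP stating which version of the age criterion is used to classify eligibility deviations.

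The cost is one deleted clause and one added sentence in the SAP. Aligning the SS needs no protocol amendment and no extra patients, visits or data. Fully reconciling the age limits in the synopsis with those in section 4.1 would mean correcting protocol text; that is a separate matter, and the SS correction does not wait on it.

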5.2.2 Protocol Deviations

All-important deviations related to study inclusion or exclusion criteria, conduct of the trial, subject managements or subject assessment will be tabulated and listed.

5.3 Missing Data

No imputation will be performed for missing data as it is a single arm study. Data that are potentially spurious or erroneous will be examined under the auspices of standard data management operating procedures.

5.4 Interim Analyses and Data Monitoring

There are no planned independent data monitoring committee (IDMC) reviews as the Carboplatin AUC-10 is considered to be relatively safer than the standard chemotherapy. However, the interim data is analysed for conference presentation.

5.5 Multi-centre Studies

This is a phase II multicentre trial. It is not expected that centre will have any effect to the primary outcomes.

5.6 Multiple Testing

[figure not shown]
No adjustment for multiple comparison will be performed.

6 Summary of Study Data

Study data will be summarised using appropriate summary statistics (i.e. mean, standard deviation, median, and range for continuous variables, and number and proportion of patients for categorical variables). Summaries will be presented for the SS population. The baseline value of any variable will be defined as the last available value prior to the first administration of study treatment.

6.1 Subject Disposition

A CONSORT diagram will be produced as follows (as applicable):

The number of patients enrolled will be tabulated by study site. Patient disposition will be tabulated, and reasons for premature discontinuation will be summarised.

6.2 Demographic and Baseline Variables

Demographic and baseline characteristics (age; primary location; stage; ECOG PS; Tumour markers; BHCG; LDH; EDTA or measured creatinine clearance will be summarised.

6.3 Concurrent Illnesses and Medical Conditions

All AEs and serious AEs (SAEs) will be coded according to the latest available Medical Dictionary for Regulatory Activities (MedDRA) version. The Chief Investigator may wish to group MedDRA codes further into more clinically meaningful groups for analysis and interpretation. Any grouping of toxicity codes will be signed off by the Chief Investigator.

6.4 Prior and Concomitant Medications

Prior and concomitant medications will be summarised in terms of frequency. Medication will be coded using Systematized Nomenclature of Medicine (SNOMED).

6.5 Treatment Compliance

Treatment compliance will be presented for all patients in the SS in terms of:

- Median and range for each cycle length.
- Frequency and percentage of patients having a dose reduction.

- Frequency and percentage of patients having a dose reduction due to low platelet count (<20).
- Frequency and percentage of patients discontinuing investigational medicinal product (IMP).
- Frequency and percentage of patients leaving the study due to disease progression or death.

7 Efficacy Analysis

7.1 General Principles

Efficacy data will be summarised using appropriate summary statistics (i.e. mean, standard deviation, median, and range for continuous variables, and number and proportion of patients for categorical variables). CIs will be calculated as appropriate. Summaries will be presented for the FAS population. The baseline value of any variable will be defined as the last available value prior to the first administration of study treatment.

7.2 Primary Efficacy Analysis

7.2.1 PFS

Kaplan-Meier (K-M) methodology will be used to estimate the median PFS. The median PFS and PFS rate for carboplatin AUC-10 at 2-years will be estimated with one-sided 95% CI to be consistent with one-sided test. However, 2-sided 95% CI will also be presented. The study result will be considered positive if the PFS rate for patients on carboplatin AUC-10 is consistent with a true difference of 15% or more from standard chemo i.e. if there are at least 39 PFS patients out of the first 45 patients at 2 years.

7.3 Secondary Efficacy Analysis

7.3.1 Metabolic Response Rate

The number and percentage of subjects falling into each response category defined in Appendix 2 of the protocol i.e. the categories of: CR, PR marker positive, PR marker negative, stable disease, and progressive disease after one cycle will be descriptively tabulated.

7.3.2 Overall response

Overall treatment responses will be measured using the same criteria described in our previous phase II study 5, which are consistent with other published reports. Progressive disease is defined as the development of new sites of disease with rising tumour markers if present. Stable disease is defined as the lack of any new sites of disease and a <90% reduction in tumour markers, 28 days after chemotherapy. Marker-positive partial response (M+ve PR) is defined as a >90% reduction in tumour markers (without normalisation) for ≥ 28 days, and no new sites of disease. Marker-negative PR (M-ve PR) is defined as a normalisation of tumour markers and no new sites of disease for ≥ 28 days. For those patients who have normal tumour markers before chemotherapy, a M-ve PR required a 50% reduction in the bi-dimensional measurements of the residual masses to be maintained for ≥ 28 days. Complete remission (CR) is defined as a normalisation of tumour markers with a complete resolution of all sites of disease. Postsurgical outcome is defined as outcome after surgery performed to remove all sites of disease, and patients who achieves a radiological CR to chemotherapy alone or has a surgically induced CR is deemed to have no evidence of disease (NED).

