**APPENDIX 2 – PET-CT RESPONSE DEFINITIONS FOR CLINICAL TRIALS\***

RESPONSE	DEFINITION	NODAL MASSES
CR	Disappearance of all evidence of disease	a. FDG-avid or PET positive prior to therapy; mass of any size permitted if PET negative b. Variably FDG-avid or PET negative; regression to normal size on CT
PR	Regression of measurable disease and no new sites	>50% decrease in SPD of up to 6 largest dominant masses; no increase in size of other nodes a. FDG-avid or PET positive prior to therapy; one or more PET positive at previously involved site b. Variably FDG-avid or PET negative; regression on CT
SD	Failure to attain CR/PR or PD	a. FDG-avid or PET positive prior to therapy; PET positive at prior sites of disease and no new sites on CT or PET b. Variably FDG-avid or PET negative; no change in size of previous lesions on CT
RELAPSED DISEASE OR PD	Any new lesion or increase by >50% of previously involved sites from nadir	Appearance of a new lesion(s) >1.5 cm in any axis, >50% increase in SPD of more than one node, or >50% increase in longest diameter of a previously identified node >1cm in short axis Lesions PET positive if FDG-avid lymphoma or PET positive prior to therapy

Abbreviations: CR, complete remission; FDG, [F] fluorodeoxyglucose; PET, positron emission tomography; CT, computed tomography; PR, partial remission; SPD, sum of produce of the diameters; SD, stable disease; PD, progressive disease.
		

\*As published in Journal of Clinical Oncology [6]

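### SAP 7.3.2 makes new sites a condition for progressive disease, so growth of a known mass can be scored as partial response or stable disease, and a marker rise without new sites as stable disease

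*SAP*

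**What the plan says.** SAP section 2 lists overall response at the end of treatment as a secondary objective, and SAP 7.3.2 gives its categories:

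- Progressive disease (PD): "Progressive disease is defined as the development of new sites of disease with rising tumour markers if present".
- Stable disease (SD): "Stable disease is defined as the lack of any new sites of disease and a <90% reduction in tumour markers, 28 days after chemotherapy".
- Partial response, marker-positive (M+ve PR): more than 90% "reduction in tumour markers (without normalisation) for ≥ 28 days, and no new sites of disease".
- Partial response, marker-negative (M-ve PR): it "is defined as a normalisation of tumour markers and no new sites of disease for ≥ 28 days". For patients with normal markers before chemotherapy, "a M-ve PR required a 50% reduction in the bi-dimensional measurements of the residual masses".
- Complete remission: markers normal and all disease sites resolved.

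The section says the criteria are those of the group's earlier phase II study.

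The protocol has two other scales. Appendix 2, the PET-CT scale, counts as PD any new lesion, or an increase of more than 50% "of previously involved sites from nadir". Appendix 3, for conventional CT response, counts as PD a marker reduction below 50%, or progression within 28 days of stopping chemotherapy.

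**The concern.** A PD category should catch every patient who is clearly getting worse, and the better categories should exclude them. In 7.3.2 the appearance of a new site is the only route into PD. The SD rule has no lower limit on marker change, so a rise satisfies it as well as a small fall does. For patients who start with raised markers, neither PR rule looks at mass size.

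At stake is how the response table can be read. In a single-arm trial with no comparator, the SD and PR rows could include patients whom the protocol's own scales would call progressive, and the PD row would be too low. If few patients progress by the end of treatment, PD is a small count, and one or two reassigned patients could remove much of it.

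**Working it through.** The SAP states no figure to reproduce here, so the check applies the 7.3.2 rules literally to each combination of baseline markers, marker course, mass course and new sites, and compares the result with the protocol.

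**No new sites**

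| Baseline markers | Marker course | Known mass | SAP 7.3.2 | Protocol Appendix 2 |
|---|---|---|---|---|
| Raised | Normalise | Grows >50% | M-ve PR | PD |
| Raised | Fall >90%, not normal | Grows >50% | M+ve PR | PD |
| Raised | Fall <90% | Grows >50% | SD | PD |
| Raised | Rise | Any course | SD | Depends on mass only |
| Normal | Stay normal | Grows >50% | SD, or none | PD |
| Normal | Become raised | Any course | SD, or none | Depends on mass only |

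The Appendix 2 column assumes that its detailed lesion-size and PET-positivity conditions are met. In the last two rows, SD follows only if no reduction at all counts as a reduction below 90%. On a stricter reading those patients have no category. No combination without a new site reaches PD.

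**New site present, baseline markers raised, no marker rise.** SD and both PR rules require no new sites, and complete remission requires all sites to have resolved, so all four are closed. PD is met only if the phrase about rising markers is read as not demanding a rise. Otherwise the patient has no category.

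**Comparison with Appendix 3.** This is the closer counterpart, since it has the same marker-positive and marker-negative PR structure.

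- A marker rise is a reduction below 50%, so it meets the Appendix 3 wording for PD. It is SD in the SAP.
- Appendix 3 lists a reduction below 50% under SD too, so it does not settle the case by itself.
- The SD marker cut-off is below 90% in the SAP and below 50% in Appendix 3. A fall of between 50% and 90% is SD in the SAP (no new sites) and meets neither the SD nor the PD marker cut-off of Appendix 3.
- Appendix 3 accepts progression as PD without requiring new sites, but gives no numerical threshold for growth.

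**Size per patient.** Overall response is analysed in the full analysis set (SAP 5.2.1.1 and 7.1). Taking that set as between the 45 evaluable and the 50 recruited patients:

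- 1/45 = 2.2 percentage points
- 1/50 = 2.0 percentage points

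This is a unit, not an estimate. The documents do not say how many patients would be affected.

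**The case against.** The strongest reply has four parts.

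1. **The criteria are a stated choice.** The SAP adopts those of an earlier study, and 7.3.2 may only summarise them. This cannot be checked: the SAP cites that study as number 5, but its reference list ends at 3. Comparability is a fair aim and is a reason to keep the old classification visible. It does not change what the current text instructs.
2. **Few patients will be affected.** Protocol 1.3 reports 2 relapses in 40 patients given AUC-10 and says most patients in the recent study eventually achieved complete response. Protocol 3.1 takes patients with no response after cycle 1 off study. This stands. Nothing in the documents suggests that mass growth with normalising markers will be common.
3. **The consequences are limited.** Overall response is in the SAP but not in the protocol's endpoint list, and protocol 11.3 calls all analyses descriptive and exploratory. SAP 6.5 also tabulates patients leaving the study for progression or death. This stands too.
4. **Appendix 2 serves another endpoint.** It is a lymphoma PET-CT scale assigned to metabolic response. This is right, and it is why the comparison with Appendix 3 matters. The two appendices still agree that PD does not need a new site.

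A reader might also infer more than the text supports:

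- **That rising markers can be scored PR.** They cannot. Both PR rules for marker-raised patients need a fall above 90% or normalisation.
- **That every error favours the treatment.** The new-site case is a gap, or PD on the looser reading, and not an upgrade.
- **That being both a responder and a PFS event is contradictory.** It is so only when both are judged at the same time. Response at the end of treatment followed by later progression is ordinary.

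**Conclusion.** The point holds for the secondary overall-response endpoint. On its literal wording, SAP 7.3.2 can score growth of a known mass as PR or SD, scores a marker rise without new sites as SD, and may leave a new site without a marker rise unclassified. The PR error is limited to patients with raised baseline markers that fall by more than 90% or normalise while a known mass grows.

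Each affected patient shifts a category rate by 2.0 to 2.2 points, assuming a denominator of 50 to 45. The total effect is unknown and probably small.

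Bias in the primary result is not shown. SAP 3.4.1.1.1 takes progression for PFS from central review and does not link it to the 7.3.2 categories, so the rule of at least 39 progression-free patients among the first 45 stands apart from this point.

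The change is still worth making. A stated rule gives the wrong category, which is different from missing detail. Leaving investigators or analysts to override it case by case, in an open-label single-arm trial, would be an unrecorded departure from the SAP.

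**What to change.** Before database lock, amend SAP 7.3.2 as follows:

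1. Define PD as any one of: a new site, whatever the markers do; growth of a known mass beyond a stated threshold, for example the increase of more than 50% from nadir already in Appendix 2; or a marker rise under a written rule that names the marker, the threshold and how the rise is confirmed. A phrase such as clearly rising would only move the ambiguity.
2. Add to SD and to both PR definitions the condition that PD is absent.
3. Say how patients with normal baseline markers are classified when their masses neither resolve nor shrink by half.
4. Reconcile 7.3.2 with protocol Appendix 3, including the 50% and 90% marker cut-offs and the duplicate use of the 50% cut-off under SD and PD.
5. Tabulate the earlier study's classification in a second column, and complete the reference for it.

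The cost is SAP wording and one extra table column. No new assessments are needed, because the end-of-treatment scan and the AFP, hCG and LDH measurements are already scheduled. This assumes that lesion measurements are recorded or can be recovered from the scans.

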## **4.0 *Eligibility, subject selection and withdrawal***

### **4.1 *Inclusion Criteria***

1. Metastatic seminoma-IGCCCG good prognosis.
2. Glomerular filtration rate by EDTA clearance over 25 ml/min (a measured creatinine clearance using Cockcroft and Gault would be allowed if unable to perform EDTA clearance).
3. ECOG Performance status 0-3.
4. Normal Alpha-fetoprotein (All levels of Human chorionic gonadotropin and Lactate dehydrogenase are acceptable).
5. Males aged  $\geq 18$  and  $\leq 75$  years.
6. Able to give written informed consent prior to study entry.
7. Patients must be sterile or agree to use adequate contraception during the period of therapy.

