### **PARTIAL RESPONSE (PR) (marker positive)**

More than 90% reduction in tumour markers and/or >50% reduction in tumour masses determined by radiology for at least 28 days following cessation of chemotherapy without normalisation of tumour markers.

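### SAP 7.3.2 scores a patient whose raised markers fall by less than 90% without normalising as stable disease however far the masses shrink, where protocol Appendix 3 gives partial response; its stable-disease rule also overlaps with PR and CR

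*SAP*

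**What the plan says.** SAP section 2 lists overall response at the end of treatment as a secondary endpoint, and SAP 7.3.2 defines its categories:

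- Marker-positive PR: "Marker-positive partial response (M+ve PR) is defined as a >90% reduction in tumour markers (without normalisation) for ≥ 28 days", with no new sites.
- Marker-negative PR: "Marker-negative PR (M-ve PR) is defined as a normalisation of tumour markers and no new sites of disease for ≥ 28 days". No minimum percentage fall is set.
- CR: "Complete remission (CR) is defined as a normalisation of tumour markers with a complete resolution of all sites of disease". Again there is no minimum fall.
- Stable disease: "Stable disease is defined as the lack of any new sites of disease and a <90% reduction in tumour markers, 28 days after chemotherapy". There is no mass criterion and no exclusion for markers that have normalised.
- Mass shrinkage enters in one place only: "For those patients who have normal tumour markers before chemotherapy, a M-ve PR required a 50% reduction in the bi-dimensional measurements".

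No order of precedence is given.

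Protocol Appendix 3 words marker-positive PR differently: "More than 90% reduction in tumour markers and/or >50% reduction in tumour masses determined by radiology for at least 28 days", in a patient whose markers have not normalised. It sets the marker limit for stable disease at a fall below 50%, where the SAP has 90%.

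On who can have raised markers, protocol 4.1 requires "Normal Alpha-fetoprotein (All levels of Human chorionic gonadotropin and Lactate dehydrogenase are acceptable"). Raised hCG or LDH at any multiple of normal is therefore allowed at entry.

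**The concern.** The two documents give different categories for the same course of disease. Under the SAP, a patient with normal LDH at baseline and masses halved is a partial responder. A patient whose LDH starts raised and ends slightly above normal, with masses 80% smaller, is stable disease. One persistently raised marker removes the scan from the classification.

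The second problem is inside SAP 7.3.2. The stable-disease rule turns on a percentage fall, while marker-negative PR and CR turn on normalisation. A patient with a modestly raised baseline can normalise with a fall well short of 90%, and so meets two or more definitions at once.

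What is at stake is the reported overall response rate. Two analysts working from the same data could report different rates, and the rate under the SAP could be lower than under the protocol's own definitions.

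**Working it through.** The plan states no figure for this rule, so there is none to reproduce. The check is algebra on one marker, followed by worked cases.

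**Notation.** Baseline = k x ULN, fractional fall = f, final value = k(1 - f) x ULN. A marker is normal when it is at or below ULN. The documents do not give the distribution of k, so a range is shown.

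**Conditions under SAP 7.3.2, no new sites**

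- Normalisation: k(1 - f) <= 1, so f >= 1 - 1/k. This gives marker-negative PR, or CR if all sites resolve.
- Marker-positive PR: f > 0.90 and k(1 - f) > 1, so 0.90 < f < 1 - 1/k. This interval exists only if 1 - 1/k > 0.90, that is k > 10.
- Stable disease: f < 0.90.

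| k (x ULN) | Fall needed to normalise | Marker-positive PR | SD only | SD and marker-negative PR (or CR) together |
|---|---|---|---|---|
| 1.5 | 33.3% | none | below 33.3% | 33.3% to <90% |
| 2 | 50% | none | below 50% | 50% to <90% |
| 3 | 66.7% | none | below 66.7% | 66.7% to <90% |
| 5 | 80% | none | below 80% | 80% to <90% |
| 8 | 87.5% | none | below 87.5% | 87.5% to <90% |
| 10 | 90% | none | below 90% | none |
| 12 | 91.7% | 90% to 91.7% | below 90% | none |
| 20 | 95% | 90% to 95% | below 90% | none |
| 100 | 99% | 90% to 99% | below 90% | none |

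**Case 1: the documents disagree.** LDH 3 to 1.2 x ULN, masses 80% smaller, no new sites, maintained for 28 days. The fall is (3 - 1.2)/3 = 60%.

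- SAP: the fall is below 90%, so it is SD. It is not marker-positive PR (60% < 90%), and not marker-negative PR or CR (1.2 > 1). The mass rule does not apply because the baseline marker was raised. Result: SD only.
- Appendix 3: masses are down by more than 50% without normalisation, so it is marker-positive PR. It is not SD or progression by marker, since both need a fall below 50%. Result: PR only.

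**Case 2: the SAP gives two answers.** LDH 1.5 to 0.9 x ULN, no new sites. The fall is 0.6/1.5 = 40%. It is below 90%, so SD is met; the marker is normal, so marker-negative PR is met. If all sites have resolved, CR is met as well.

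**Case 3: the same baseline, three results.** At k = 5:

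- A 70% fall ends at 5 x 0.30 = 1.5 x ULN: SD only.
- An 82% fall ends at 5 x 0.18 = 0.9 x ULN: SD and marker-negative PR (or CR) together.
- A 92% fall ends at 5 x 0.08 = 0.4 x ULN: marker-negative PR (or CR), not SD.

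**Case 4: a high baseline.** At k = 15, an 85% fall ends at 15 x 0.15 = 2.25 x ULN. This is SD under the SAP even if masses have shrunk by more than 50%.

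**Weight of one patient.** 1/45 = 2.2 percentage points; with all 50 recruited patients in the analysis set it would be 1/50 = 2.0.

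**The case against.** A reader might infer that, because marker-positive PR is empty at or below 10 x ULN, responders with modestly raised markers are in general scored as stable disease. The documents do not support that. Patients whose markers normalise reach marker-negative PR or CR, and normalising takes a smaller fall when the baseline is lower (33.3% at 1.5 x ULN). At or below 10 x ULN every fall above 90% normalises the marker, so the empty category is not an error in itself. Nor is 10 x ULN the cause, as case 4 shows. The cause is the missing mass-reduction route.

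The emptiness also depends on reading the rule for one marker, or as binding on every raised marker. The SAP speaks of markers in the plural and does not say how hCG and LDH combine. If one may supply the 90% fall while the other stays raised, the category can be reached below 10 x ULN.

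The SAP's choice may be deliberate: it says it follows the criteria of the group's previous phase II study. That is a legitimate reason to keep the old scale available. It does not remove the conflict with the protocol on which the SAP says it is based, or the overlap within 7.3.2.

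Appendix 3 is not a clean standard either. LDH falling from 1.5 to 1.05 x ULN (30%) with masses 80% smaller meets its marker-positive PR, but also the marker limits of its stable and progressive disease, both set at a fall below 50%. Such a patient cannot be used to show that the protocol gives PR and the SAP does not; case 1 can.

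Finally, the endpoint is secondary in the SAP, is not listed in protocol 2.1 or 11.1, has no threshold or test, and belongs to analyses that protocol 11.3 calls descriptive. Protocol 1.3 reports that most patients in the earlier study eventually reached CR, which gives no sign that the affected group is large. All of this limits the weight of the point, but leaves the rule in need of correction.

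**Conclusion.** The point holds in this form. Under SAP 7.3.2, a patient with raised baseline markers that fall by less than 90% and stay raised, with no new sites, is stable disease regardless of mass shrinkage. Appendix 3 can make the same patient a partial responder. Separately, a patient who normalises with a fall below 90% meets stable disease together with marker-negative PR or CR, and the SAP does not say which prevails. On the single-marker reading, marker-positive PR is also unattainable at baselines at or below 10 x ULN, but that is a side effect.

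The number affected cannot be computed, because the documents give neither the distribution of baseline markers nor the share that fall without normalising. The share with raised markers below 10 x ULN would be the wrong count, since it includes patients correctly scored CR or marker-negative PR. Each reclassified patient moves the rate by 2.2 points at n = 45. The primary rule of 39 out of 45, and the number of cycles, which protocol 3.1 bases on PET-CT, are not affected. The matter should be corrected before analysis, but it does not threaten the primary conclusion.

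**What to change.** Reconcile SAP 7.3.2 with Appendix 3 before database lock:

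1. **Restore the mass route.** Marker-positive PR: markers not normalised, no new sites, and either a marker fall above 90% or a reduction above 50% in the bi-dimensional mass measurements, held for at least 28 days.
2. **State how hCG and LDH combine.** Use only the markers raised at baseline. One workable rule is that normalisation requires all of them to be normal, and the 90% fall must be met by each. Another rule would do if written down in advance.
3. **Fix the order.** Check progression first, then CR, marker-negative PR and marker-positive PR. Stable disease applies only when none of these is met.

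Case 1 then becomes marker-positive PR, and case 2 marker-negative PR or CR. Case 4 becomes marker-positive PR if masses are down by more than 50%, and otherwise stays stable disease.

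Do not import Appendix 3 wholesale, because its stable and progressive disease share the same marker limit.

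The cost is SAP wording only. Markers at end of treatment and follow-up, the end-of-treatment scan, and the later CT for residual masses are already in protocol 5.3.2 and 5.4. The downside is a small departure from the earlier study's scale; tabulating response on that scale alongside keeps the comparison.
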